3.3 Outcome measurement

The questionnaire, administered during the base- and endline of the project, includes four substantive sections. The first section (A) administers demographic questions (e.g., gender, religion, etc.). The second section (B) administers questions pertaining to knowledge about sexual and reproductive health. This includes family planning (B1), condoms (B2), HIV/Aids (B3), other STIs (B4). The third section (C) administers questions about self-reported behavior. This includes sex (C1), HIV testing (C2), and access of youth-friendly corners (C3). The final section, only asked during the endline, includes questions about the JIC.

3.4 Endline

Endline data collection will happen approximately six months after the JIC implementation and will administer the same questions to the same grades identified at baseline. At this point, the endline is scheduled to take place in October 2017.

14 Empirical Analysis

Our primary outcomes of interest are knowledge and self-reported behavior. To assess the degree to which the JIC improved both outcomes, we will create an overall index that standardizes all our outcome variables. This includes all questions in sections B1, B2, B3, and B4. In section C, this includes all questions, but question C1-8. In a second step, we will split the overall index into a self-reported behavior (section A and B), and a knowledge index (section C). In a third step, we will split the index further into the following topics: family planning knowledge (B1), condom knowledge (B2), HIV/Aids knowledge (B3), STIs knowledge (B4), sex behavior (C1), self-reported testing behavior (C2), and self-reported health access behavior (C3). To account for the networked nature

of the trial, we estimate the overall effects, total effects, spillover effects, and direct effects of the JIC on our main index and on our sub-indexes, separately for the three targeting strategies and across targeting strategies.

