3.1 Baseline

The baseline data collection, conducted by a team of 10 trained enumerators divided into 3 groups, lasted about two months from March 16, 2017 to April 11, 2017 and from May 24, 2017 to July 11, 2017 for a total of 52 days. Data collection had to be interrupted during the month of April due to a month-long school break. The survey instrument is attached to this document. The prime reason for the baseline survey—in addition to collecting outcomes before the intervention takes place—was to map the entire friendship network in a given grade (more below).

Once data collection started, the survey team found additional ineligible schools that were either unreachable by car, did not have the targeted grades or were closed. Overall, the survey team managed to conduct a baseline in 98 out of the 102 schools in the treatment group (96% of the target), 28 out of 34 schools in the control 1 category, and 7 out of 34 in control 2. The final sample, thus, consists of 133 schools for the baseline survey. 37 of the schools are in Livingstone and 96 schools in Choma. 19 schools are secondary schools and 114 are primary schools. All students in either grade 6 (if primary school) or grade 11 (if lower secondary school) present on the day of baseline were interviewed for a total of 8,276 students.

Since some instruments are sensitive in nature (more below), we opted to administer self-administered surveys on tablet computers supported by ACASI (audio-assisted computerized assisted self-interview software) technology. Specifically, the survey was loaded unto the tablets and each question was accompanied by an audio file that read out loud the question in the desired language (options were Tonga and English). Students were given headphones for increased privacy. After hearing the question, students were to tap on the relevant answer. Finding the correct answer was facilitated by a) maximizing the number of questions with a vignette or picture or color coded, and by

b) positioning the answers on the left, middle, or right panel of the tablet and have the audio file explain where to find the answer. Two enumerators were present to help and assist in case of confusion or any other problem.

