3.2 Network mapping

The network mapping was done as follows. First, enumerators collected attendance lists at every school for the assigned grade. Second, enumerators administered the survey, which included the following question: "Now, I want to know who are the friends that you spend time with in your grade. I am going to read you the names of all students in your grade. For every name, I want you tell me if the student is a friend of yours that you spend time with." Enumerators then recorded each friend of a given respondent on a separate list.

In a third step, the list was then passed on to the principal investigator (PI). In treatment group 1, a random subset of students was chosen for treatment. In treatment group 2, the PI used the R package *keyplayer* (An [and](#) Liu, [2016](#)), to identify the students with the highest in-degree centrality D_i , defined as the sum of incoming friendship nominations from the rest of the network. Specifically, $D_i = \sum_j w_{ji}$, where w_{ji} indicates friendship nominations from j to i . In treatment group 3, the PI used the same package to identify students with the highest edge betweenness centrality. It is defined as:

$$B^i = \sum_k g_{jk}^i, \text{ where } g_{jk}^i \text{ is the number of shortest paths between students } j \text{ and } k, \text{ and}$$

g_{jk}^i gives the amount of those paths running through student i . In other words, key-player selects the group of students who, combined as a pair, are directly connected to the highest number of different students compared to any other combination. The code underlying this procedure, including all realized assignments, is available upon request.

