B2-7	Condoms cannot help against sexually transmitted infections.	1	2	3

	Section B3: HIV and AIDS Now, we are going to ask you a few questions about HIV/AIDS.			
B3-1	Have you ever heard of HIV/AIDS?	Yes → B4		
	Please tell me whether you think the statement about HIV/AIDS is true, or false, or whether you don't know.			
		True	False	Don't Know

B3-2	You can see whether a person has HIV/AIDS.	1	2	3
B3-3	It is possible to cure AIDS.	1	2	3
B3-4	Sleeping with a virgin can cure AIDS.	1	2	3
B3-5	A mother can transmit HIV to her child when she is pregnant.	1	2	3
B3-6	You can get AIDS by sharing food with a person who has AIDS.	1	2	3
B3-7	You can get AIDS because of witchcraft.	1	2	3
B3-8	You cannot get HIV the first time you have sex.	1	2	3
B3-9	You can get HIV through kissing.	1	2	3
B3-10	A healthy person cannot get AIDS.	1	2	3
B3-11	AIDS can be transmitted by mosquitos.	1	2	3
B3-12	Everybody is going to get AIDS at some time in his or her life.	1	2	3

Section B4: Sexually transmitted infections (STIs)

Next, we want to ask you about sexually transmitted diseases other than HIV/AIDS.

B4-1	Have you ever heard about sexually transmitted diseases other than HIV/AIDS?	Yes No → C		
Please tell me whether you think the statement about sexually transmitted diseases is true, or false, or whether you don't know.				
		True	False	Don't know
B4-2	In Zambia, only sex workers have sexually transmitted diseases.	1	2	3
B4-3	You can always see if somebody has a sexually transmitted disease.	1	2	3
B4-4	Male circumcision reduces the risk of getting sexually transmitted diseases.	1	2	3
B4-5	Sexual transmitted diseases can cause infertility	1	2	3
B4-6	Sexually transmitted disease can never be cured.	1	2	3

	Please tell me whether you think it is true or false if a person can get tested for sexually transmitted diseases at the following places.			
		True	False	Don't Know
B4-7	Public clinic	1	2	3
B4-8	Private clinic	1	2	3
B4-9	In church	1	2	3
B4-10	Some NGO clinics	1	2	3
B4-11	Drug shop	1	2	3
B4-12	Gas station	1	2	3
B4-13	At the witch doctor	1	2	3

Section C: Self-reported behavior

Section C1: Sex

Now, we are going to ask you direct questions regarding your sexual experiences. If a question makes you feel uncomfortable, you can skip the question.

C1-1	In the last six months, did you visit a health clinic to talk about issues relating to sex or family planning?	Yes → C1-3 No

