C1-2	When was that?	1 month ago 2 or 3 months ago 3-6 months ago 6-12 months ago More than 12 months ago
C1-3	In the past 6 months, have you been to the health facility as a patient?	Yes No
C1-4	(Only males) Are you circumcised?	Yes → C1-6 No
C1-5	When were you circumcised?	1 month ago 2 or 3 months ago 3-6 months ago 6-12 months ago More than 12 months ago
C1-6	Have you ever had sexual intercourse?	Yes → C1-8 No → C1-7

C1-7	What is the main reason that you have not had sex? → After, move to section C2.	No opportunity yet No sex before marriage Afraid of getting pregnant Afraid of getting diseases I want to be abstinent Don't know
C1-8	What was the main reason you have had sex?	Married Love Fun/curiosity Friend influenced me I received money in return I wanted to get pregnant I was forced Don't know
C1-9	How many sexual partners have you had in the last 12 months?	0 1 3-5 More than 5
C1-10	Do you have a steady sexual partner?	Yes No
C1-11	The last time you had sex, did you or your partner use a condom?	Yes No → C1-13.
C1-12	Do you use condoms every time you have sex?	Yes No
C1-13	Are you currently using any family planning method or contraception?	Yes No

Section C2: HIV testing Now, we are going to ask you questions about HIV testing.		
C2-1	Have you ever been tested for HIV?	Yes No → C3
C2-2	In the last six months, have you been tested for HIV?	Yes No → C3

C2-3	How many months ago was that?	1 month ago 2 or 3 months ago 3-6 months ago 6-12 months ago
C2-4	Do you know your test result?	Yes No

Section C3: Youth-friendly corners

Now, we have two questions about youth-friendly corners.

C3-1	Have you ever heard of a youth friendly corner at the health facility?	Yes → No D
C3-2	In the past 12 months, have you visited a youth friendly corner at the health facility?	Yes No

Section D: JIC (endline only)

Now, we have a few questions about the Join in Circuit (JIC).

D1	Are you currently wearing a wristband from the JIC?	Yes No
D2	Have you participated in a Join-In Circuit run in the last six months?	Yes → D5 No
D3	Have you heard about the Join-In-Circuit?	Yes No
D4	Did any of your friends talk to you about the JIC or things they learned at the JIC? → After question, skip to D12	Yes No
D5	On a scale from 1 to 5, how interesting did you find the JIC? 1 means you didn't find it interesting at all and 5 means you found it very interesting.	Number _____

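### An endline about six months after the JIC cannot fall in October 2017 for schools whose baseline ran from May 24 to July 11

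*SAP*

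**What the plan says.** Section 3.4 gives the follow-up twice. As an interval: "Endline data collection will happen approximately six months after the JIC implementation". As a date: "the endline is scheduled to take place in October 2017", marked there as the position at the time of writing.

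Section 3.1 dates the baseline "from March 16, 2017 to April 11, 2017 and from May 24, 2017 to July 11, 2017 for a total of 52 days", and gives one of its purposes as "collecting outcomes before the intervention takes place". Section 3.2 explains that each school's friendship list went to the principal investigator, who then picked the students for all three treatment arms. No JIC dates appear anywhere in the SAP.

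The same questionnaire is used at baseline and endline. Three items look back six months: C1-1 ("In the last six months, did you visit a health clinic to talk about issues relating to sex or family planning"), C1-3 (attendance at a health facility as a patient) and C2-2 ("In the last six months, have you been tested for HIV"). Section 4 puts every section C question except C1-8 into the overall index, then splits that index into knowledge and behaviour. The section letters attached to those two sub-indexes look transposed. I take section C as behaviour, as the instrument labels it.

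**The concern.** A school's JIC cannot run before its students have been mapped and selected. Any school mapped "from May 24, 2017 to July 11, 2017" therefore starts its follow-up no earlier than late May and, at the end of the window, no earlier than mid-July. October is too soon for six months to have passed.

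Two things are at stake. First, a paper that reports effects at about six months would misdescribe the estimate for an unknown share of schools, and a shorter interval changes what can be said about persistence. Second, a student asked in October about the last six months will report visits and tests that happened before the JIC, which the JIC could not have caused.

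**Working it through.** **Inputs.** Baseline windows from section 3.1: March 16 to April 11 and May 24 to July 11, 2017. Endline month from section 3.4: October 2017, taken as October 1 to 31. Earliest possible JIC date for a school: its own baseline day (sections 3.1 and 3.2). One month = 30.4375 days.

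**Step 1: longest possible follow-up.** Interval = endline date minus baseline date. The result is an upper bound, because the JIC may have come later.

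| Baseline day | Endline Oct 1 | Endline Oct 31 |
|---|---|---|
| March 16 | 199 d = 6.54 mo | 229 d = 7.52 mo |
| April 11 | 173 d = 5.68 mo | 203 d = 6.67 mo |
| May 24 | 130 d = 4.27 mo | 160 d = 5.26 mo |
| July 11 | 82 d = 2.69 mo | 112 d = 3.68 mo |

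The stated six months is attainable for first-window schools if the JIC followed baseline closely. No second-window school reaches it, even with a same-day JIC and an October 31 endline. If the JIC began only after all baselines were finished, no school would exceed 3.68 months.

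**Step 2: endline date that would deliver six months.** May 24 plus six months is November 24, 2017. July 11 plus six months is January 11, 2018. Both are earliest dates.

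**Step 3: share of a six-month recall window that precedes the JIC.** With m months of follow-up the share is 1 − m/6. For m = 5.26 it is 12%; for m = 2.69 it is 55%.

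**Step 4: what that does to the comparison.** For an item scored as any event in the window, the arm difference equals the post-JIC difference multiplied by the probability of no event before the JIC. That probability is the same in both arms in expectation, and near 1 when events are uncommon. The absolute difference is thus almost intact, and what changes is the variance. Let λ be the monthly event rate and δ the monthly effect, with rare events:

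- six-month window: standardised effect ≈ δm / √(6λ)
- window of exactly m months: standardised effect ≈ δm / √(mλ)
- ratio of the first to the second = √(m/6)

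| m (months) | √(m/6) | Loss |
|---|---|---|
| 5.26 | 0.94 | 6% |
| 4.27 | 0.84 | 16% |
| 3.68 | 0.78 | 22% |
| 2.69 | 0.67 | 33% |

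**Step 5: weight in the indexes.** The instrument has 17 + 7 + 12 + 13 = 49 section B questions and, without C1-8, 12 + 4 + 2 = 18 section C questions. The three six-month items are 3 of 67 (4.5%) in the main index and 3 of 18 (17%) in the behaviour index. Assume equal item weights and equal standardised item effects, and ignore any change in the index's own variance. Then even the 33% loss lowers the main index effect by about 0.33 × 3/67 = 1.5% and the behaviour index effect by about 0.33 × 3/18 = 5.5%.

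**The case against.** The best defence of the text is that it hedges twice: the interval is approximate, and the October date is provisional. That could stretch to the single most favourable second-window case, 5.3 months. It does not stretch to 2.7 to 3.7 months. A provisional date is a reason to correct the sentence while that is still cheap.

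The defence is stronger on the consequences, and most of it stands. A reader might infer three further things that the SAP does not support.

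- *That 12 to 55% of the effect on the recall items is lost to contamination.* That share is mainly exposure time missing against a full six months, which no rescoring can restore. Pre-JIC events fall equally on both arms in expectation, so they add variance only.
- *That most schools are affected.* The second window holds 35 of the 54 weekdays in the two date ranges (65%), but schools per window are not reported, and the SAP's own count is 52 days.
- *That the twelve-month items C1-9 and C3-2 are part of the problem.* Their recall window would be half pre-JIC even with exactly six months of follow-up, so the date conflict is not the cause.

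The obvious remedy, rescoring everything to a three-month window, is not clearly an improvement either. By the formula in step 4 it helps only when m/√6 is below √3, that is m < √18 = 4.2 months. At m = 6 it cuts the standardised effect by 1 − √(3/6) = 29%. It would also be longer than the 2.69 months available to a July 11 school surveyed on October 1.

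**Conclusion.** The two statements in section 3.4 contradict each other for every second-window treatment school. The result needs only the SAP's own dates and the fact that selection follows baseline. Follow-up there is at most 4.3 to 5.3 months for a May 24 school and 2.7 to 3.7 months for a July 11 school. How many schools this covers, and how much shorter follow-up really is, cannot be settled without JIC dates.

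The effect on the analysis is secondary. In these schools three behaviour items lose roughly 6 to 33% of their standardised effect against a fully exposed window. This assumes rare events, even rates, a same-day JIC and the same endline timing across arms; a later JIC makes the loss larger. It is lost precision and gives no ground for suspecting a spurious effect. Knowledge items have no recall window, so for them only the stated length of follow-up is wrong.

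**What to change.** **Reconcile section 3.4 in one of two ways.** Either restate follow-up as the range the dates allow and describe effects as measured at that interval, or move the provisional endline so that six months is reached. For second-window schools that means no earlier than November 24, 2017 to January 11, 2018, depending on baseline day, and later if the JIC did not follow at once. A later date must be checked against the school calendar, which the SAP does not give. The order of visits should not differ by arm.

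**Record JIC and endline dates for each school** and report the distribution of actual intervals by arm.

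**Leave the questionnaire and the primary index as they are**, which keeps comparability with baseline. Add one pre-specified sensitivity behaviour index that omits C1-1, C1-3 and C2-2. Where the timing answers in C1-2 and C2-3 allow, it could instead count only events inside the school's recorded JIC-to-endline interval, with the same window applied to control schools. Three limits need stating in advance: C1-3 has no timing question, the answer categories are coarse and overlap at three months, and the skip instruction at C1-1 should be checked to confirm that students who answer yes do reach C1-2.

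**Cost.** A few sentences, two dates per school, one extra analysis and a less favourable stated follow-up. Moving the endline instead costs time and field logistics.

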1. For each of the three targeting strategies, what is the overall effect of the JIC on all students?

2. For each of the three targeting strategies, what is the total effect of the JIC on participating students?

3. For each of the three targeting strategies, what is the spillover effect of JIC on non-participating students?
4. What is the most effective targeting strategy to maximize the above effects?

12 Design

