4.3 Network estimands

Guided by the same hypotheses as above, we also estimate total, spillover, and direct effects of the JIC on the same outcomes, and compare them across targeting strategies. We estimate the total effect of the JIC on targeted students separately for the three targeting strategies analogous to equation (1), except that we now restrict the samples to treated students in treated schools and comparable untreated students in control schools.⁴ We estimate the spillover effect of the JIC on non-targeted students separately for the three targeting strategies analogously to equation (1), except that we now restrict the samples

⁴Specifically, under random targeting, we compare randomly targeted students in treated schools to all students in untreated schools; under indegree targeting, we compare treated students in indegree-treated schools to the corresponding share of highest-indegree students in untreated schools; under edge-centrality targeting, we compare treated students in edge-centrality schools to the corresponding share of highest edge-centrality pairs in untreated schools.

to untreated students in treated schools and comparable untreated students in control schools. We estimate the direct effect of the JIC on targeted students under random targeting, except that we now restrict the sample to students in random-targeted schools, and estimate

$$Y_{ij} = \beta_0 + \beta_1 T_{ij} + \beta_2' X_{ij} + \epsilon_{ij},$$

where T_{ij} is an indicator equal to 1 if student i in random-targeted school j is treated and 0 otherwise.

The direct effect compares treated students in treatment schools to comparable un-treated students in treated schools. By comparing treated to untreated students in the same school, this effect removes the indirect effect via peers. Note: in our study, however, the direct effect can only be estimated with random targeting, because only with random targeting are treated and untreated students in a given school comparable to each other.

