6.2 Survey instrument

Section X. Logistics and Network Measurement

Questions to be asked and/or filled in by enumerator.

X1	Fill in the name of the school	Name of school _____
X2	Fill in the ID of the school	School ID _____
X3	Ask student: What is your first name? Confirm with student that name was spelled correctly	Student first name _____
X4	Ask student: What is your last name? Confirm with student that name was spelled correctly	Student last name _____
X5	Enter ID of student from enrollment roster	Student ID _____
X6 (baseli ne AND endlin e!)	
Ask student: Now, I want to know who are the friends that you spend time with in your grade. I am going to read you the names of all students in your grade. For every name, I want you tell me if the student is a friend of yours that you spend time with.
 
[Prompt: Slowly read through enrollment list and prompt for answer at every name (pause, look, "is this a friend that you spend time with?"). Whenever student labels individual friend, put down number on the right.]
 
Protocol for AIR: At every school, obtain enrollment protocol from school officials. The protocol needs to be numbered such that every student has a unique ID. Each enumerator then gets one sheet. This requires making copies (by hand or electronically). AIR should write up a protocol on how this is undertaken.
	ID 1 _____ ID 2 _____ ID 3 _____ ID 4 _____ ID 5 _____ ID 6 _____ ID 7 _____ ID 8 _____ ID 9 _____ ID 10 _____ ID 11 _____ ID 12 _____ ID 13 _____ ID 14 _____

Section A. Demographic Characteristics

First, we have some general questions about your background.

A1	What day, month and year were you born?	Day	Month	Year
A2	What is your gender?	Male		
A3	What grade are you in?	Number	_____	
A4	What is your religion?	Islam		
		Catholic		
		Apostolic		
		Pentecostal		

		Anglican Christian, other Other Don't know
A5	What is your father's primary job?	Farmer ...
A6	Does your father have a hard time reading (e.g., a newspaper or a letter)?	Yes No
A7	Can your father write in English?	Yes No
A8	Are your parents married to each other?	Yes No
A9	What is your native language?	Nyanja Lozi Tonga Kaonde English Luvale Lunda Other Don't know

Section B: Knowledge about sexual and reproductive health				
Section B1: Family planning / contraceptives				
Now, we have some questions about contraception. By that we mean ways in which one can avoid getting pregnant.				
B1-1	Have you heard of family planning before?	Yes No		

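### Endline students who were never in the JIC draw would be counted as untreated, which can bias the random-targeting direct effect and, less strongly, the total and spillover effects

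*SAP*

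**What the plan says.** At baseline, SAP section 3.1 covers the students in the assigned grade who were "present on the day of baseline were interviewed for a total of 8,276 students". For the mapping, section 3.2 reports that "enumerators collected attendance lists at every school for the assigned grade". The instrument in section 6.2 (item X6) points to a different list: "At every school, obtain enrollment protocol from school officials". Item X5 also takes the student ID from the enrolment roster. After the mapping the list went to the principal investigator, who chose a random subset of students in treatment group 1. The plan does not say which list was the frame for that draw.

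At endline, section 3.4 "will administer the same questions to the same grades identified at baseline". The target is the grade, not the listed students.

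In section 4.3 the direct effect uses the students in random-targeted schools, with `T_ij` equal to 1 for a treated student and 0 for anyone else. The spillover sample is the untreated students of JIC schools. The random-arm total effect compares targeted students with every student in control schools (footnote 4). The direct effect is limited to random targeting because "only with random targeting are treated and untreated students in a given school comparable to each other".

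The groups are named in more than one way. Section 1 defines them by participation ("For each of the three targeting strategies, what is the spillover effect of JIC on non-participating students"), while section 4.3 and its footnote use both targeted and treated.

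**The concern.** Random selection makes selected and unselected students comparable only among those who could have been selected. Every selected student was on the list. A student outside it who answers the endline questionnaire can only be counted as untreated in a JIC school, or as part of the comparator in a control school. No sentence excludes or flags such students.

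If they score differently from listed students, for instance because they attend less or have just moved school, the direct effect picks up that difference. The random-arm total effect picks up part of it through the control schools, and the spillover effect picks up the difference between the two dilutions.

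The unsettled meaning of treated adds a second route. Item D2 records self-reported participation, so coding by participation is possible. A selected student who missed the JIC would then move into the spillover sample, while in the two centrality arms the total-effect comparator is still built from who would have been selected.

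Robustness check 2, randomization inference, also needs the frame for the direct effect, because a student with no chance of selection cannot be permuted.

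**Working it through.** **Baseline count.** Section 3.1 gives 98 + 28 + 7 = 133 schools. The two other splits agree (37 + 96 = 133 and 19 + 114 = 133). Mean interviewed per school: 8,276 / 133 = 62.2.

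**Inputs**
- Listed students per school: N = 62.2, taken as the size of the draw frame.
- Selected: s = 30. Section 1 sets at least 30, or 20% in larger schools; 20% of 62.2 is 12.4, so 30 applies.
- Listed but unselected: 62.2 − 30 = 32.2.
- m, the off-list share of the endline grade: not in the plan. Assumed 5%, 10% and 21.3%. The last is an upper illustration from the Table 1 mean of 79.0 students: (79.0 − 62.2) / 79.0 = 0.213. The plan warns that this variable is noisy, and it covers 169 schools rather than the 133 surveyed.
- d, the score gap of off-list against listed students: not in the plan. Assumed −0.1, −0.2 and −0.4 SD.
- Random-targeting schools: 34 as assigned (section 2.2). Baseline reached 98 of 102 JIC schools, so the number may be slightly lower.

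**Formulas** (no true effect, no covariates)
- Off-list students per school: N × m / (1 − m)
- Their share of the untreated: q = off-list / (32.2 + off-list)
- Direct-effect bias = −q × d
- Random-arm total-effect bias = −m × d
- Random-arm spillover bias = (q − m) × d, taking all control students as comparator

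**Results** (in SD; the three values are for d = −0.1, −0.2, −0.4)

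| m | Off-list per school | q | Direct | Total | Spillover |
|---|---|---|---|---|---|
| 5% | 3.3 | 9.2% | +0.009, +0.018, +0.037 | +0.005, +0.010, +0.020 | −0.004, −0.008, −0.017 |
| 10% | 6.9 | 17.7% | +0.018, +0.035, +0.071 | +0.010, +0.020, +0.040 | −0.008, −0.015, −0.031 |
| 21.3% | 16.8 | 34.3% | +0.034, +0.069, +0.137 | +0.021, +0.043, +0.085 | −0.013, −0.026, −0.052 |

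For example, at m = 10%: 62.2 × 0.10 / 0.90 = 6.9; 6.9 / (32.2 + 6.9) = 0.177; 0.177 × 0.2 = 0.035.

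**Against sampling error.** With unit SD, the standard error of the direct effect is about √(1/(34 × 30) + 1/(34 × 39.1)) = 0.042 at m = 10%. By normal approximation the false-positive rate at a nominal 5% is 5.5% (m = 5%, d = −0.1), 14% (m = 10%, d = −0.2) and 41% (m = 21.3%, d = −0.2). A simulation with 34 schools, 62 listed and 30 selected students per school and school-clustered standard errors (1,500 runs per setting) gave 15% and 43% for the last two.

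**After restriction to the list.** q = m = 0, so the bias is zero by algebra. In the simulation the restricted estimate was 0.00 SD, with 4.5% to 6.7% rejection across settings.

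**The case against.** **The frame is inferred.** Much of the evidence favours the enrolment roster: items X5 and X6 both use it, and the network question reads out the names of everyone in the grade. An attendance list may simply mean a class register. A reader might infer from section 3.1 that baseline absentees had no chance of selection; the documents do not establish this. If the roster was the frame, absentees were in the draw and only later joiners are affected. This stands, and the 21.3% illustration, which treats the shortfall from Table 1 as off-list students, would then not apply.

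**The analysis set is read from silence.** Section 3.4 says where the questionnaire goes, not who enters section 4.3. That section asks for comparable untreated students, and for the two centrality arms footnote 4 picks total-effect controls by network rank, which requires having been mapped. So the total-effect exposure is mainly in the random arm. Calling students comparable does not, however, supply an inclusion rule.

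**The covariates may exclude these students.** Section 4.1 calls the covariates pre-treatment. If they come from baseline, students without a baseline record drop out of the adjusted models. But section 3.3 has section A asked in both rounds, and the plan does not say which round is used. Robustness check 1 and the strategy comparisons in section 4.3 use no covariates, so the students stay in. Check 1 would then change the sample as well as the model. The direct effect, being estimable in one arm only, has no strategy comparison. For the total and spillover effects, differences between strategies would partly cancel if the JIC arms had similar off-list shares and gaps.

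**The sizes are assumed.** This stands. A 5% share with a 0.1 SD gap gives a bias of about 0.01 SD, well under one standard error.

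**Conclusion.** The gap is real. Followed literally, the plan counts students who were never in the draw as untreated, against its own reason for trusting the direct effect. Later joiners are in this position under either list; baseline absentees are as well if the attendance list was the frame.

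A reader might go further and conclude that the random-targeting comparisons are broken. The documents do not support that. The bias depends on an off-list share and a score gap that the plan does not give, and baseline covariates might remove these students from the adjusted models. Under the assumed 5% to 21% share and 0.1 to 0.4 SD gap, the bias is +0.01 to +0.14 SD for the direct effect, +0.005 to +0.09 SD for the random-arm total effect and −0.004 to −0.05 SD for spillover. The signs assume that off-list students score lower; with no gap all three are zero.

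Exposure is clearest in the analyses without covariates, and in the adjusted models if section A is taken from endline. The overall and targeting effects (H1 and H2) are not affected by this mechanism, because such students occur in all arms and no within-school split is used. This should be settled before endline data are analysed, so that the sample is not chosen after the fact.

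**What to change.** - **Sections 3.2 and 6.2:** reconcile the attendance list with the enrolment roster and state which was the frame for the draw.
- **Sections 3.4 and 4.3:** restrict the direct, total and spillover samples to students on that list, matched by roster ID (X5). In control schools, where no draw took place, use the same type of baseline list.
- **Section 4.3:** define `T_ij` and every treated or untreated group by selection, so that selected students who missed the JIC stay in the treated group.
- **Section 4.1, footnote 3:** state that section A covariates come from baseline.
- **Reporting:** keep the whole endline grade for H1 and H2, and report off-list endline students separately by arm.

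The cost is wording. Roster IDs are in the instrument, and section 3.2 says that the realised assignments are available. There are two small downsides: fewer untreated students in these analyses, and effects of being selected rather than of taking part. Questions 2 and 3 in section 1 should be reworded to match.
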